8.6.5.3.3 EQ-5D

The items of EuroQoL-5D questionnaire (mobility, self care, usual activities, pain discomfort and anxiety depression) will be analysed according to the EQ-5D-3L user guide¹⁹. All item responses will be transformed in responses of three levels and two levels, as follows:

- Three levels: no problems, some problems and extreme problems
- Two levels: no problems and problems.

Descriptive statistical analyses by time-point will be performed for three levels response and for two levels response (as a continuous and as a categorical variable). Also, analyses by means of MMRM model with a previous rank transformation will be applied using three and two levels.

VAS EQ-5D will be analysed by the same MMRM.

8.6.5.3.4

FACT-Hep

Questionnaire FACT-Hep (version 4)²⁰ on clinical status included 45 items, 27 of which will be used for the determination of the following scale scores:

- Subscales:
 - Physical Well-Being subscale, PWB
 - Social/Family Well-Being subscale, SWB
 - Emotional Well-Being subscale, EWB
 - Functional Well-Being subscale, FWB
 - Hepatobiliary Cancer subscale, HCS
- FACT-G Total Score, FACTG
- FACT-Hep Trial Outcome Index (TOI)
- FACT-Hep total score

The individual items will be described as a continuous and as a categorical variable (see section 8.6.1) by time-point.

The subscales and the different total scores will be also described as a continuous variable and the MMRM will be applied.

8.6.5.3.5

EORTC-QLQ-C30

Questionnaire EORTC-QLQ-C30 (version 3)²¹ included 30 items and all of them will be used for the determination of the following scale scores:

- Global health status/QoL, QL2
- Functional scales:
 - Physical functioning, PF2
 - Role functioning, RF2
 - Emotional Functioning, EF
 - Cognitive functioning, CF
 - Social functioning, SF
- Symptom scales
 - Fatigue, FA
 - Nausea and vomiting, NV
 - Pain, PA
 - Dyspnoea, DY
 - Insomnia, SL
 - Appetite loss, AP
 - Constipation, CO
 - Diarrhoea, DI
 - Financial difficulties, FI

The individual items will be described as a continuous and as a categorical variable (see section 8.6.1) by time-point.

The scales scores will be also described as a continuous variable and the MMRM will be applied.

8.6.5.3.6

EORTC QLQ-HCC18

Questionnaire EORTC-QLQ-HCC18²² is a supplementary questionnaire module to be employed in conjunction of QLQ-C30 (is a Hepatocellular Carcinoma Module), included 18 items and all of them will be used for the determination of the following scale scores:

- Symptom scales

- Fatigue, FATI
- Body image BI
- Jaundice, JAUN
- Nutrition, NUTR
- Pain, PA
- Fever, FEV
- Single items
 - Abdominal swelling, AB
 - Sex life, SX

The individual items will be described as a continuous and as a categorical variable (see section 8.6.1) by time-point.

The scale scores will be also described as a continuous variable and the MMRM will be applied.

8.6.5.3.7

Adverse events

A summary of treatment-emergent adverse events (AEs), including the number of events reported, the number and percentage of patients reporting at least one event of each of the following:

- Any AE
- Any severe AE (grade greater or equal to 3 in the NCI CTCAE v5.0)
- Any AEs (CTCAE) ≥ 3 excluding palmar-plantar erythrodysthesia
- Any treatment-related AE (with cabozantinib)
- Any severe treatment-related AE
- Any AE with outcome of death
- Any serious AE
- Any treatment-related serious AE
- Any AE leading to discontinuation of the treatment permanently (cabozantinib)
- Any treatment-related AE leading to discontinuation of the treatment permanently (regorafenib, nivolumab or both)

The number and percentage of patients who experience one or more treatment-emergent AEs as well as the number of AE episodes will be tabulated by body system, preferred term (according to MedDRA v21.1), seriousness, intensity, action taken, outcome, relationship to the study drug and NCI CTCAE v5.0.

8.6.5.3.8

Concomitant medication

The concomitant medication after randomization will be described by time-point and study product. Concomitant medication and its characteristics will be listed. The number of patients with at least concomitant medication globally and by ATC code (according to ATC classification index with the last version of WHO-DD at the end of last patient follow-up) will be described.

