| | PHYSICAL WELL-BEING | Not at all | A little bit | Some-what | Quite a bit | Very much |
|-----|--|------------|--------------|-----------|-------------|-----------|
| GP1 | I have a lack of energy | 0 | 1 | 2 | 3 | 4 |
| GP2 | I have nausea | 0 | 1 | 2 | 3 | 4 |
| GP3 | Because of my physical condition, I have trouble meeting the needs of my family | 0 | 1 | 2 | 3 | 4 |
| GP4 | I have pain | 0 | 1 | 2 | 3 | 4 |
| GP5 | I am bothered by side effects of treatment | 0 | 1 | 2 | 3 | 4 |
| GP6 | I feel ill | 0 | 1 | 2 | 3 | 4 |
| GP7 | I am forced to spend time in bed | 0 | 1 | 2 | 3 | 4 |
| | SOCIAL/FAMILY WELL-BEING | Not at all | A little bit | Some-what | Quite a bit | Very much |
| GS1 | I feel close to my friends | 0 | 1 | 2 | 3 | 4 |
| GS2 | I get emotional support from my family | 0 | 1 | 2 | 3 | 4 |
| GS3 | I get support from my friends | 0 | 1 | 2 | 3 | 4 |
| GS4 | My family has accepted my illness | 0 | 1 | 2 | 3 | 4 |
| GS5 | I am satisfied with family communication about my illness | 0 | 1 | 2 | 3 | 4 |
| GS6 | I feel close to my partner (or the person who is my main support) | 0 | 1 | 2 | 3 | 4 |
| Q1 | Regardless of your current level of sexual activity, please answer the following question. If you prefer not to answer it, please check this box  and go to the next section. | | | | | |
| GS7 | I am satisfied with my sex life | 0 | 1 | 2 | 3 | 4 |

Sponsor's code: ACTION

EudraCT No: 2019-004991-20

Version: 4.0

Date: 15 July 2021

CONFIDENTIAL

By circling one (1) number per line, please indicate how true each statement has been for you during the past 7 days.

| | EMOTIONAL WELL-BEING | Not at all | A little bit | Some-what | Quite a bit | Very much |
|-----|---|------------|--------------|-----------|-------------|-----------|
| GE1 | I feel sad | 0 | 1 | 2 | 3 | 4 |
| GE2 | I am satisfied with how I am coping with my illness | 0 | 1 | 2 | 3 | 4 |
| GE3 | I am losing hope in the fight against my illness | 0 | 1 | 2 | 3 | 4 |
| GE4 | I feel nervous | 0 | 1 | 2 | 3 | 4 |
| GE5 | I worry about dying | 0 | 1 | 2 | 3 | 4 |
| GE6 | I worry that my condition will get worse | 0 | 1 | 2 | 3 | 4 |

| | FUNCTIONAL WELL-BEING | Not at all | A little bit | Some-what | Quite a bit | Very much |
|-----|--|------------|--------------|-----------|-------------|-----------|
| GF1 | I am able to work (include work at home) | 0 | 1 | 2 | 3 | 4 |

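### The SAP's count of 27 FACT-Hep scoring items covers only the four well-being subscales and FACT-G, and leaves none for the Hepatobiliary Cancer subscale it also lists

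*SAP*

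**What the plan says.** SAP 8.6.5.3.4 states that the questionnaire "included 45 items, 27 of which will be used for the determination of the following scale scores". Eight scores follow: physical (PWB), social/family (SWB), emotional (EWB) and functional (FWB) well-being, "Hepatobiliary Cancer subscale, HCS", the FACT-G total, the TOI, and the "FACT-Hep total score". The section then plans item-by-item description, and both descriptive statistics and the repeated-measures model (MMRM) for the subscales and totals. SAP section 9.2 reserves Tables 32 to 34 for items, subscales and total scores.

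The SAP cites the instrument's validation paper, but gives no item allocation, no formula for any score and no definition of the TOI. The form itself is printed in Protocol section 14.6 (Appendix 7). For the two EORTC questionnaires (SAP 8.6.5.3.5 and 8.6.5.3.6), the matching sentences say that every item is used for scoring.

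**The concern.** The SAP sets a number of scoring items and a list of scores that do not fit together. If 27 items are all that may be used, and the four well-being subscales already use 27, nothing remains for the HCS. The statement reads as an operative scoring rule, because the parallel EORTC sentences use the same construction to say how many items feed the scores, and planned tables depend on it. A programmer who follows it cannot produce the HCS, and would produce either no FACT-Hep total or a copy of FACT-G. A programmer who ignores it departs from the SAP with no record of the reason.

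**Working it through.** **Inputs.** Rated items counted on the form in Protocol section 14.6, each scored 0 to 4:

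| Block on the form | Item codes | Items |
|---|---|---|
| Physical well-being | GP1–GP7 (last: "I am forced to spend time in bed") | 7 |
| Social/family well-being | GS1–GS7 (last: "I am satisfied with my sex life"; the opt-out box before it is not a rated item) | 7 |
| Emotional well-being | GE1–GE6 | 6 |
| Functional well-being | GF1–GF7 | 7 |
| Additional Concerns | C1–C6, Hep1, CNS7, Cx6, H17, An7, Hep2–Hep6, HN2, Hep8 | 18 |

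**Step 1: the SAP's total.** 7 + 7 + 6 + 7 + 18 = 45. The stated 45 is reproduced.

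**Step 2: the SAP's 27.** 7 + 7 + 6 + 7 = 27. Among all combinations of the five blocks, this is the only one that sums to 27. It covers PWB, SWB, EWB and FWB, and FACT-G taken as their sum.

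**Step 3: what is left for the HCS.** 27 − 27 = 0 items. The items outside the four well-being blocks number 45 − 27 = 18, or 18/45 = 40% of the form. They are the only items not already assigned to a well-being subscale.

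**Step 4: could another set of 27 work?** The SAP does not name its 27 items. Suppose all 18 Additional Concerns items were among them. Then 27 − 18 = 9 items would remain for four well-being subscales that hold 27 on the form. More generally, if the five subscales use the five printed blocks, they need all 45 items, so any selection of 27 leaves at least one listed subscale incomplete.

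**Step 5: the FACT-Hep total.** The maximum raw sum is 27 × 4 = 108 for 27 items and 45 × 4 = 180 for 45 items. A FACT-Hep total from the 27 well-being items would be the same number as FACT-G, yet the SAP lists the two as separate scores.

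**Step 6: the TOI.** Neither document says which subscales it contains. If it includes the HCS, it fails for the reason in step 3. If it uses well-being subscales only, it can be scored from the 27.

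**The case against.** The best defence is that this is one wrong number in an introductory clause. All 45 items are administered, and the same section plans to describe each one. It lists the HCS and FACT-Hep total separately from FACT-G and cites the validation paper, so the author plainly meant to score them. A programmer would notice the conflict at once and could resolve it at any time without new data. All of that stands, and it limits the consequence. It does not make the sentence right: no other text in either document supplies a scoring rule that overrides the 27.

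A second objection is that the form heads its last block Additional Concerns, not HCS, and that neither document says all 18 items enter the HCS. That is also fair. The mapping is a strong inference, because no other items are left, but the allocation should be stated from the instrument's scoring rules.

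Three stronger readings are tempting:

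- A reader might infer that three of the eight scores, including the TOI, cannot be produced. The documents support this for the HCS and the FACT-Hep total. For the TOI they do not, because its composition is never given.
- A reader might infer that the scores which justify choosing FACT-Hep are lost. The documents give no reason for choosing it, and disease-specific quality of life is also covered by the EORTC QLQ-HCC18, for which all 18 items are scored.
- A reader might infer that data will be missing. They will not; the 18 items are left out of the scoring sentence, not out of data collection.

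**Conclusion.** The point holds as an internal inconsistency in the SAP. The stated 27 scoring items match the four well-being subscales and FACT-G, so five of the eight listed scores can be made as written. The HCS cannot, and the FACT-Hep total would collapse into FACT-G. The TOI remains open.

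This rests on three assumptions: that the 27 are the four well-being blocks (the only block match), that FACT-G and the FACT-Hep total are sums over their blocks, and that the Additional Concerns block is the source of the HCS.

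The importance is low. Quality of life is an exploratory objective (Protocol section 2, SAP 6.3), and SAP 8.6 declares the analysis non-inferential. No FACT-Hep score enters the sample size, the interim rule, or any primary or secondary endpoint.

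**What to change.** In SAP 8.6.5.3.4, replace the clause limiting scoring to 27 items with a statement that all 45 are used: 27 for PWB (7), SWB (7), EWB (6), FWB (7) and FACT-G, and the 18 Additional Concerns items for the HCS and every score that includes it. Confirm this allocation against the instrument's scoring rules. In the same edit, name the components of the TOI, the reverse-scored items and the rule for missing items within a subscale.

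The cost is one corrected sentence and a short scoring table. No data collection, visit, sample size or other analysis changes. It should be made before the FACT-Hep scores are programmed, so that the derivation follows the written plan.

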8.7 POST-HOC STATISTICAL ANALYSIS

No subgroup analyses are planned in the protocol.

Due to clinical relevance in this study of the first-line treatment a subgroup analysis is required by sponsor for the following groups:

- Sorafenib as first-line treatment
- Other than sorafenib as first-line treatment

The analyses related to the non confirmatory primary endpoints (PEPs) and secondary endpoints will be also performed by subgroup.

9 TABLES

For the table of safety variable and other efficacy variables (where applicable according to section 8.7) the results will be present for all subjects and by subgroup classification (within the same table).

9.1 Demographic characteristics, screening and baseline.

- Table 1. Study population.
- Table 2. Informed consent.
- Table 3. Demographic data and vital signs.
- Table 4. Clinical characteristics at HCC diagnosis.
- Table 5. Clinical characteristics at study entry.
- Table 6. Comorbidities. Number (%) of subjects reporting one or more Comorbidity (globally and by type of comorbidity).
- Table 7. First line treatment.
- Table 8. Selection criteria.

9.2 Safety variables and other efficacy variables.

- Table 9. **Primary outcomes.** Rate of AEs, SAEs, related-AEs, AEs leading to discontinuation, deaths and AEs (CTCAE) ≥ 3 excluding palmar-plantar erythrodysthesia.
- Table 10. **Secondary outcomes.** ORR and time to ORR.
- Table 11. **Secondary outcomes.** Overall survival.
- Table 12. **Secondary outcomes.** Time to progression (TTP)
- Table 13. **Secondary outcomes.** Pattern of progression.
- Table 14. **Secondary outcomes.** Post-progression survival.
- Table 15. **Secondary outcomes.** Rate of patient who develop new extrahepatic spread.
- Table 16. **Duration of response.**
- Table 17. BCLC staging system and CHILD-PUGH scale.
- Table 18. Tumor disease assessment (including tumor size).
- Table 19. Central test and stool test. Samples Yes/No.
- Table 20. Tumor biopsy.
- Table 21. Physical examination.
- Table 22. General examinations: vital signs, ECOG and oxygen saturation.
- Table 23. Laboratory test. Urinalysis.
- Table 24. Laboratory test. Hematology.
- Table 25. Laboratory test. Biochemistry and electrolyte.
- Table 26. Laboratory test. Thyroid functions.
- Table 27. Laboratory test. Specific laboratory test.
- Table 28. EQ-5D. Individual items.
- Table 29. EQ-5D. Three level items.
- Table 30. EQ-5D. Two level items.
- Table 31. EQ-5D. EQ VAS.
- Table 32. FACT-Hep. Directly items.
- Table 33. FACT-Hep. Subscales.
- Table 34. FACT-Hep. Total scores.
- Table 35. EORTC-QLQ-C30. Directly items.

Table 36. EORTC-QLQ-C30. Subscales.

Table 37. EORTC QLQ-HCC18. Directly items.

Table 38. EORTC QLQ-HCC18. Subscales.

Table 39. Exitus.

Table 40. Survival status variables.

Table 41. Cabozantinib treatment information.

Table 42. Visit control. Last visit by patient.

Table 43. Screen failure information.

Table 44. End of treatment.

Table 45. End of study.

Table 46. Concomitant medication. Number (%) of subjects reporting one or more concomitant medication (globally and by type ATC code).

Table 47. Adverse events. Summary of number (%) of subjects reporting one or more AE, severe AE, AE (CTCAE)≥3 excluding palmar-plantar erythrodysthesia, treatment-related AE, severe treatment-related AE, AE with death, serious AE, treatment-related serious AE, AE leading to disc., treatment-related AE leading to disc.

Table 48. Adverse events. Number (%) of subjects reporting one or more treatment-emergent adverse events (in general and by System Organ Class).

Table 49. Adverse events. Number (%) of subjects reporting one or more treatment-emergent adverse events and number of AE occurrences by body system and preferred term.

Table 50. Adverse events. Number (%) of subjects reporting one or more treatment-emergent adverse events and number of AE occurrences by seriousness.

Table 51. Adverse events. Number (%) of subjects reporting one or more treatment-emergent adverse events and number of AE occurrences by severity.

Table 52. Adverse events. Number (%) of subjects reporting one or more treatment-emergent adverse events and number of AE occurrences by action taken.

Table 53. Adverse events. Number (%) of subjects reporting one or more treatment-emergent adverse events and number of AE occurrences by causality.

Table 54. Adverse events. Number (%) of subjects reporting one or more treatment-emergent adverse events and number of AE occurrences by outcome.

Table 55. Adverse events. Number (%) of subjects reporting one or more treatment-emergent adverse events and number of AE occurrences by severity, seriousness and causality.

Table 56. Adverse events. Number (%) of subjects reporting one or more treatment-emergent adverse events and number of AE occurrences by NCI CTCAE v5.0.

Table 57. Protocol deviations. Number (%) of subjects reporting one or more protocol deviation.

10 LISTINGS

Listing 1. Study population.

Listing 2. Informed consent.

Listing 3. Demographic data and vital signs.

Listing 4. Clinical characteristics at HCC diagnosis.

Listing 5. Clinical characteristics at study entry.

Listing 6. Comorbidities.

Listing 7. First line treatment.

Listing 8. Selection criteria.

Listing 9. **Primary outcomes.** Rate of AEs, AE (CTCAE) ≥ 3 excluding palmar-plantar erythrodysthesia, SAEs, related-AEs, AEs leading to discontinuation, deaths.

Listing 10. **Secondary outcomes.** ORR, time to ORR, time to progression, pattern of progression, Overall and post-progression survival and rate of patients who develop new extrahepatic spread. BCLC staging system and CHILD-PUGH scale.

Listing 11. Duration of response

Listing 12. Tumor disease assessment (including tumor size).

Listing 13. Central test and stool test.

Listing 14. Tumor biopsy.

Listing 15. Physical examination.

Listing 16. General examinations: vital signs, ECOG and oxygen saturation.

Listing 17. Laboratory test. Urinalysis.

Listing 18. Laboratory test. Hematology.

Listing 19. Laboratory test. Biochemistry and electrolyte.

Listing 20. Laboratory test. Thyroid functions.

Listing 21. Laboratory test. Specific laboratory test.

Listing 22. EQ-5D.

Listing 23. FACT-Hep.

Listing 24. EORTC QLQ-C30

Listing 25. EORTQ QLQ-HCC18

Listing 26. Exitus.

Listing 27. Survival status variables.

Listing 28. Cabozantinib treatment information.

Listing 29. Visit control.

Listing 30. Screen failure information.

Listing 31. End of treatment.

Listing 32. End of study.

Listing 33. Subsequent treatments

Listing 34. Concomitant medication.

Listing 35. Adverse events.

Listing 36. Protocol deviations.

11 FIGURES

Figure 1. Overall survival. Survival plot.

Figure 2. Time to progression. Survival plot.

Figure 3. Post-progression survival. Survival plot.

Figure 4. Post-progression survival by pattern of progression. Survival plot.

Figure 5. Relative change in tumor size. Spider plot.

Figure 6. Best change in tumor size. Waterfall plot.

Figure 7. Time to response. Swimmer plot.

Figure 8. Duration of response. Survival plot.

